6.1.2 Secondary Efficacy Endpoints

Time to PSA Progression

For patients with PSA declines, the PSA progression date is defined as the date that a $\geq 25\%$ increase and an absolute increase of $\geq 2 \mu\text{g/L}$ (2 ng/mL) above the nadir is documented, which is confirmed by a second consecutive value obtained 3 or more weeks later.

For patients with no PSA declines, the PSA progression date is defined as the date that a $\geq 25\%$ increase and an absolute increase of $\geq 2 \mu\text{g/L}$ (2 ng/mL) above the baseline is documented, which is confirmed by a second consecutive value 3 or more weeks later. Baseline is defined as last PSA measurement prior to first dose.

Time to PSA progression is defined as the PSA progression date minus date of first dose + 1, which will be censored in the following scenarios:

- If patient does not have any PSA progression, it will be censored at last PSA sample date.
- If patient does not have post baseline PSA assessment, it will be censored at Day 1.
- If patient took any new anti-cancer therapy before any PSA event, the time to PSA progression will be censored at the PSA sample date prior to the date of new anti-cancer therapy.

Overall Survival Rate at 1 Year

Overall Survival is defined date of death due to any cause minus date of first dose +1. If a patient has not died, overall survival is censored at the last known alive date.

The last known alive date will be derived based on the maximum of last known alive dates in the survival follow up CRF page, last visit, or last SAE onset date.

Overall survival rate at 1 year is defined as the corresponding Year 1 (Day 365) Kaplan-Meier estimate on survival curve.

Time to first use of a subsequent antineoplastic therapy

Time to first use of a subsequent antineoplastic therapy is defined as date of the first systemic antineoplastic therapy minus first dose date +1. If a patient has not started the antineoplastic therapy, the time to event analysis is censored at the last dose date of study medication.

PSA response

PSA response is defined in below categories:

- PSA30 (maximum decline of $\geq 30\%$ decline from baseline at lowest post baseline)
- PSA50 (maximum decline of $\geq 50\%$ decline from baseline at lowest post baseline)
- PSA90 (maximum decline of $\geq 90\%$ decline from baseline at lowest post baseline)

Objective response rate

Objective Response Rate (ORR) is the proportion of patients whose best overall response is Complete Response (CR) or Partial Response (PR) per RECIST 1.1. Only patients with measurable disease at baseline will be included in the analysis of ORR.

Best Overall Response is derived based on the time point response information on the CRF according to RECIST criteria for both subjects with measureable and non-measureable disease:

- CR
- PRNon Cr/Non Pd
- SD
- NE

The derivation of BOR is implemented using SAS based solely on investigator assessed information across all timepoints. Confirmation of response is not required according to the protocol.

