- If enzalutamide co-administration with warfarin cannot be avoided, additional INR monitoring should be conducted.
- Enzalutamide is an inhibitor of human P-glycoprotein (P-gp) and may increase
 exposure to medicines that are P-gp substrates. Medicinal products with a narrow
 therapeutic range that are substrates for P-gp (e.g., digoxin, colchicine, dabigatran
 etexilate) should be used with caution when administered concomitantly with
 enzalutamide.

No other new systemic therapy or new radiotherapy for treatment (exception for spinal cord compression, pain management, etc.) for prostate cancer is permitted while subject is on the study. Subjects with pre-existing non-target lesions (e.g., bone metastases) receiving palliative radiography for pain treatment before participation in the study are allowed to continue receiving radiotherapy during the study.

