5.3.4 Survival Follow-up

For all subjects, survival status and subsequent anti-cancer therapies will be followed every 12 weeks for a maximum of 3 years from first dose. The study will end when the last subject has been followed for 1 year from date of first dose.

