Subjects that discontinue study drug for a reason other than radiographic progression or initiation of a new anti-neoplastic therapy will have a PSA test performed 30 days from date of last dose and undergo long-term follow-up every 12 weeks from date of last dose. Long term follow-up will assess for survival, subsequent anti-neoplastic therapy for prostate cancer and radiographic progression. Subjects will be followed for a maximum of 3 years from first dose. The study will end when the last subject has been followed for 1 year from date of first dose. Radiographic imaging will end when the patient has developed a radiographic progression, or initiated subsequent anti-neoplastic therapy. Reasonable effort should be made to contact any subject lost to follow-up during the course of the study in order to complete study related assessments and retrieve any outstanding data and study drug. Following unsuccessful telephone contact, an effort to contact the subject by mail using a method that provides proof of receipt should be attempted. Such efforts should be documented in the source documents.

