7.4.2 Analysis of Secondary Endpoints

The overall survival rate at 1 year will be estimated via Kaplan-Meier methodology with censoring defined by the time of last contact with the subject for those subjects who do not have a reported death. This analysis will be repeated in each subset defined by prior treatment with exposure.

For patients with PSA declines, the PSA progression date is defined as the date that a $\geq 25\%$ increase and an absolute increase of $\geq 2~\mu g/L$ (2 ng/mL) above the nadir is documented, which is confirmed by a second consecutive value obtained 3 or more weeks later. For patients with no PSA declines, the PSA progression date is defined as the date that a $\geq 25\%$ increase and an absolute increase of $\geq 2~\mu g/L$ (2 ng/mL) above the baseline is documented, which is confirmed by a second consecutive value 3 or more weeks later. The time to PSA progression will then be estimated via Kaplan-Meier methodology with censoring defined by the time of the last available PSA measure. This analysis will be repeated in each subset defined by prior treatment with exposure.

The proportion of subjects achieving a maximum PSA decline from baseline of at least 30% (PSA30), 50% (PSA50), and 90% (PSA90), respectively, and having an objective response will provided along with 90% confidence intervals. Analyses for PSA response rates will include all subjects with at least one post-baseline PSA measure. Analysis for objective response will include all subjects with measurable disease at baseline. These analyses will be repeated in each subset defined by prior treatment with exposure.

The time to first use of a subsequent antineoplastic therapy will be estimated via Kaplan-Meier methodology with censoring defined by the time of last contact with the subject for those subjects who do not have a reported use of antineoplastic therapy. This analysis will be repeated in each subset defined by prior treatment with exposure.

The analysis described in Section 7.4.1.3 will be repeated for secondary endpoints as appropriate.

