1 INTRODUCTION

This Statistical Analysis Plan (SAP) contains a more technical and detailed elaboration of the principal features of the analysis described in the protocol for study 9785-MA-1008, and includes detailed procedures for executing the statistical analysis of the primary and secondary endpoints and other data.

The SAP is finalized and signed prior to database hard lock, or accumulation of substantial amount of data in an open-label study to ensure lack of bias. If needed, revisions to the approved SAP may be made prior to database hard lock. Revisions will be version controlled.

This statistical analysis is coordinated by the responsible biostatistician of APGD-US. Any changes from the analyses planned in the SAP will be justified in the Clinical Study Report (CSR).

Prior to database hard lock, a final review of data and TLFs meeting will be held to allow a review of the clinical trial data and to verify the data that will be used for analysis set classification. If required, consequences for the statistical analysis will be discussed and documented. A meeting to determine analysis set classifications may also be held prior to database hard lock.

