- j The window for all radiological assessments is ± 7 days. At Weeks 9, 17, 25 and subsequent assessments prior to treatment discontinuation, all other procedures must be completed within the ± 3 day window. Bone progression at the first reassessment at Week 9 requires a confirmatory scan 6 or more weeks later.
- k Adverse events, serious or non-serious, will be collected from the time the patient signs the consent form until the Safety Follow-Up visit, regardless of initiation of another anti-neoplastic therapy prior to last dose of enzalutamide.
- l Long-term follow-up for radiographic progressions (until progression or initiation of new anti-neoplastic therapy), survival, and subsequent anticancer therapies should be performed every 12 weeks for a maximum of 3 years from first dose. The study will end when the last subject has been followed for 1 year from date of first dose.
- m Enzalutamide will be administered until the disease progression, including radiographic progression or unequivocal clinical progression. Per the Investigator's clinical judgment and with sponsor approval, patients may be allowed to continue enzalutamide until the next treatment is initiated. If another non-cytotoxic, non-investigational, antineoplastic agent is initiated after protocol-defined progression has been determined, enzalutamide may be continued per the Investigator's clinical judgment and with sponsor approval as long as the patient is tolerating enzalutamide and continues androgen deprivation therapy
- n Blood samples for CTC molecular profiling and serum samples will be collected at baseline, week 13, time of PSA progression, and time of radiographic progression.

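### Time to first subsequent antineoplastic therapy is censored at last dose in the SAP but at last contact in the protocol; for the same events the SAP median can only be equal or shorter

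*SAP*

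**What the plan says.** Time to first use of a subsequent antineoplastic therapy is a secondary endpoint in both documents, estimated by Kaplan-Meier.

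- **Censoring, protocol.** Section 7.4.2 specifies "censoring defined by the time of last contact with the subject for those subjects who do not have a reported use of antineoplastic therapy".
- **Censoring, SAP.** Section 6.1.2 specifies: "If a patient has not started the antineoplastic therapy, the time to event analysis is censored at the last dose date of study medication".
- **Event, SAP.** Section 6.1.2 takes "date of the first systemic antineoplastic therapy minus first dose date +1". Protocol 7.4.2 does not restrict the event to systemic therapy.
- **Estimator.** SAP 7.4.2 applies the primary-endpoint method (Kaplan-Meier median with 90% CI) and says nothing further on censoring.
- **Status of the SAP.** Its introduction calls it "a more technical and detailed elaboration of the principal features of the analysis described in the protocol". Neither the text nor the revision history mentions a change to this rule. The commitment to justify changes in the study report covers departures from the SAP, so it would not pick up this one.
- **Follow-up after the last dose.** Protocol 5.3.4 says that, for all subjects, "survival status and subsequent anti-cancer therapies will be followed every 12 weeks for a maximum of 3 years from first dose". SAP section 2, footnote l, says the same of "survival, and subsequent anticancer therapies should be performed every 12 weeks for a maximum of 3 years from first dose".

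**The concern.** The two rules differ for every subject who stops enzalutamide and has no new therapy recorded afterwards. Under the SAP such a subject leaves the risk set on the last dose date, even if he is then followed for months without new therapy. A subject who stops on the same day and starts new therapy later stays in the risk set until that start. Whether off-drug time counts thus depends on what happens later, which makes the censoring informative. The endpoint describes what follows study treatment, yet the rule discards the therapy-free time after treatment that the study plans to collect.

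At stake is which median and 90% CI are reported for one secondary endpoint. A reader of the protocol would expect one estimator and receive another, shifted in a known direction if the events are the same.

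**Working it through.** Neither document gives a figure for this endpoint, so there is nothing to reproduce. The direction can be proved. The size can only be illustrated.

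**1. Direction.** The Kaplan-Meier estimate is S(t) = Π(1 − d_j/n_j) over event times up to t. With the same events, every d_j is unchanged. Last dose is never later than last contact, so every n_j under the SAP rule is equal or smaller. Hence S_SAP(t) ≤ S_protocol(t) throughout, and the SAP median is equal or shorter. In 40,000 random data sets with ties there were no violations, under either of two conventions for the median.

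**2. Worked example.** Ten subjects: new therapy at months 3, 5, 7, 9 and 11. Five others have none, with last doses at months 1, 2, 4, 6 and 8 and last contacts at months 12 to 16.

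| Month | Protocol n | Protocol S | SAP n | SAP S |
|---|---|---|---|---|
| 3 | 10 | 0.90 | 8 | 0.875 |
| 5 | 9 | 0.80 | 6 | 0.729 |
| 7 | 8 | 0.70 | 4 | 0.547 |
| 9 | 7 | 0.60 | 2 | 0.273 |
| 11 | 6 | 0.50 | 1 | 0 |

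The median is 11 months under the protocol rule and 9 under the SAP rule.

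**3. Size with a fixed share never starting therapy.** All inputs are assumed: median time on drug 4 or 6 months; median gap from last dose to new therapy 1, 2 or 4 months; never-starters followed to death (median 8 months after last dose) or cut-off; 12 to 24 months of follow-up. Each scenario had 200,000 simulated subjects, with the same events under both rules.

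| Never start | Shortening of median | Same, half of starters with no gap | Fall in 12-month therapy-free estimate |
|---|---|---|---|
| 0-5% | 0-8% | 0-5% | 0-7 points |
| 10% | 4-10% | 4-7% | 3-8 points |
| 20% | 9-14% | 9-13% | 5-10 points |
| 40% | 22-27% | 23-28% | 9-15 points |

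At the planned N = 40 (4 months on drug, gap 2 months; 4,000 replicates), the typical within-trial shift in the median is 0 to 0.1 months with up to 10% never starting. With 20% it is 0.65 months (5th-95th percentile 0 to 2.6), and with 40% it is 2.4 months. The last figure excludes 173 replicates in which the protocol median was not reached. With 20% never starting, the protocol-rule median itself ranges from 6.4 to 11.7 months (5th-95th percentile).

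**4. Size when death competes with new therapy for everyone.** Assumed: median 4 months on drug, mean 15 months from last dose to death, exponential times. The implied never-share, ignoring cut-off, is gap/(gap + 15). Medians are in months.

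| Mean gap | Never-share | Protocol | SAP | Shortening | Death-free median | 50% cumulative incidence |
|---|---|---|---|---|---|---|
| 2 | 2/17 = 12% | 6.5 | 6.4 | 0.1/6.5 = 2% | 6.2 | 6.8 |
| 3 | 3/18 = 17% | 7.6 | 7.3 | 0.3/7.6 = 4% | 7.2 | 8.2 |
| 6 | 6/21 = 29% | 10.6 | 9.4 | 1.2/10.6 = 11% | 9.9 | 12.3 |
| 12 | 12/27 = 44% | 15.6 | 11.7 | 3.9/15.6 = 25% | 14.5 | not reached |

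**5. The ordering needs the same events.** Protocol 5.1.3.2 reads "No other new systemic therapy or new radiotherapy for treatment (exception for spinal cord compression, pain management, etc.) for prostate cancer is permitted", so some radiotherapy can occur on study. Suppose the protocol wording counted such treatment and the SAP did not. Ten subjects stop at month 4: three have non-systemic treatment at month 5 and systemic at month 9, five have systemic therapy at month 8, and two are untreated to month 12. At month 8 the protocol estimate is 0.7 × 2/7 = 20% and the SAP estimate is 3/8 = 37.5%. The order reverses.

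**The case against.** The strongest reply is that the consequence is small and that the protocol rule is not shown to be more accurate.

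- **Size.** The percentages in step 3 are high for modest never-shares, because subjects due to start therapy cannot die first. Where death competes for everyone, shortening is 2% at a 12% never-share and 4% at 17%. Protocol 5.1.5 lets drug continue until the next treatment, which narrows the gap. At N = 40 the typical shift is small against sampling error. All of this stands.
- **Accuracy.** Both rules as worded censor subjects who die untreated, and neither treats death as a competing event. Against the death-free median in step 4, the SAP rule is nearer in three of four cases. Against cumulative incidence, the protocol rule is nearer. This also stands: the better rule depends on an estimand that neither document states. The case for last contact rests on conformity with the protocol and on not letting the later outcome decide whose off-drug time counts.
- **Systemic.** The word is probably a clarification, since Protocol 3.3 and 5.1.3.2 list radiotherapy separately from antineoplastic or systemic treatment. Step 5 is therefore a conditional wording point.
- **Follow-up.** Protocol 6.1 also plans to follow "subsequent anti-neoplastic therapy for prostate cancer and radiographic progression", but only for subjects who stop for reasons other than radiographic progression or new therapy. The availability of data therefore rests mainly on Protocol 5.3.4 and SAP footnote l, which are not limited in that way.

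None of this reconciles the two censoring dates.

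**Conclusion.** The concern holds. The documents prescribe different censoring dates for one secondary endpoint, and nothing in either resolves or explains it. For the same events, the SAP median is equal to or shorter than the protocol median; this is certain. The amount is not derivable from the documents. On the assumed inputs it runs from nil, when next therapy is prompt, to roughly a quarter of the median when about 40% never start new therapy. Shorter here means relative to the protocol rule, which is itself biased when subjects die untreated.

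The endpoint is descriptive, with no test or decision rule attached, and primary rPFS and the sample size are untouched. It should be corrected, but it does not threaten the main result.

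**What to change.** In SAP 6.1.2, replace the last-dose censoring date with the date of last contact, as in Protocol 7.4.2. Preferably define this as the last contact at which the subject was known to be free of new therapy; that is a suggested clarification, not protocol text. Use one event wording in both documents, with or without the restriction to systemic therapy. If last-dose censoring is deliberate, record it as a change from the protocol and give the reason. Cumulative incidence with death as a competing event could be added as a supportive analysis.

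The cost is one or two sentences. The follow-up for new therapy is already planned, the SAP already derives a last known alive date for overall survival in the same section, and SAP section 1 allows revision before database hard lock.

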2.2 Study Design and Dose Rationale

2.2.1 Study Design

This is a US-based, multicenter, open-label, single-arm, study evaluating the efficacy, safety, and tolerability of open-label enzalutamide in the re-treatment setting. A total of 40 patients will be enrolled. Patients must have been previously treated with enzalutamide in the pre-chemotherapy setting for a minimum of 8 months, followed by docetaxel and/or cabazitaxel for a minimum of 4 cycles. Exposure to intervening systemic anti-cancer therapies such as abiraterone prior to chemotherapy is allowed. Subjects will receive treatment with open-label enzalutamide (160 mg daily), administered as four 40 mg capsules, by mouth, once daily, until radiographic or clinical progression (such as pathological

fracture, cord compression, worsened pain requiring radiation therapy, or opioid analgesic dose increase or initiation), or unacceptable toxicity. Per the Investigator's clinical judgment and with sponsor approval, patients may be allowed to continue enzalutamide until the next treatment is initiated. If another non-cytotoxic, non-investigational, antineoplastic agent is initiated after protocol-defined progression has been determined, enzalutamide may be continued per the Investigator's clinical judgment and with sponsor approval as long as the patient is tolerating enzalutamide and continues androgen deprivation therapy.

The consensus guidelines of the Response Evaluation Criteria in Solid Tumors (RECIST) 1.1 and the Prostate Cancer Clinical Trials Working Group 2 (PCWG2) will be utilized to determine radiographic disease progression. Radiographic disease progression is defined by RECIST 1.1 for soft tissue disease. Bone disease progression is considered when a minimum of two new lesions are observed. Progression on bone scan at time points prior to or at Week 9 requires a confirmatory scan performed six or more weeks later. This confirmatory scan should demonstrate at least 2 additional new lesions compared to the Week 9 scan (PCWG2).

The following assessments of prostate cancer status will be collected during the course of the trial: soft tissue disease on computed tomography (CT) scan or on magnetic resonance imaging (MRI), bone disease on radionuclide bone scans, and PSA.

Study films (CT/MRI and bone scan) should be read on site. Each site should ideally designate the same reader who will evaluate the images for any one subject for the duration of the trial.

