5.1.3.2 Concomitant Treatment (Medication and Non-Medication Therapy)

Concomitant medications will be captured from the Screening Visit through 30 days after last dose.

Prohibited Medications

The following medications are prohibited while patients are on enzalutamide treatment and have not had disease progression:

- Chemotherapy with anti-tumor activity against prostate cancer such as cabazitaxel, mitoxantrone, etc.
- Sipuleucel-T
- Rad-223
- Androgen-receptor antagonists (bicalutamide, flutamide, nilutamide)
- 5α-reductase inhibitors (finasteride, dutasteride)
- Estrogens
- Cyproterone acetate
- Androgens (testosterone, dehydroepiandrosterone [DHEA], etc.)
- Ketoconazole
- Abiraterone acetate
- Any other investigational agent

Restricted Medications

The dosage and regimen of the following medications and any chronic permitted medications should be stabilized during the screening period (> 4 weeks prior to randomization) and held constant throughout the study:

- Denosumab and bisphosphonates
- GnRH agonist/antagonist therapy

There is a potential for enzalutamide to affect exposures to other medicinal products, or for other medicinal products to affect exposure to enzalutamide:

Strong CYP2C8 inhibitors (e.g., gemfibrozil) or CYP2C8 inducers (e.g., rifampicin)
are to be avoided. If subject must be co-administered a strong CYP2C8 inhibitor, the
dose of enzalutamide should be reduced to 80 mg once daily. If a co-administration of

- the strong inhibitor is discontinued, the enzalutamide dose should be returned to the dose used prior to initiation of the strong CYP2C8 inhibitor.
- Strong CYP3A4 inducers (e.g. carbemezapine, phenobarbital, phenytoin, rifampin) or moderate CYP3A4 inducers (e.g. bosentan, efavirenz, etravirine, modafinil, nafcilin, St. John's Wort) should be avoided if possible as they may reduce enzalutamide plasma concentration if co-administered. Selection of a concomitant medication with no or minimal CYP3A4 induction potential is recommended.
- Enzalutamide is a strong inducer of CYP3A4 and a moderate inducer of CYP2C9 and CYP2C19. Medicinal products with a narrow therapeutic range that are substrates of CYP3A4 (e.g. alfentanil, cyclosporine, dihydroergotamine, ergotamine, fentanyl, pimozide, quinidine, sirolimus, tacrolimus), CYP2C9 (e.g. phenytoin, warfarin), CYP2C19 (e.g. S-mephenytoin), or UGT1A1 should be avoided if possible, as enzalutamide may decrease their exposure.

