6.1 Efficacy Endpoints

6.1.1 Primary Efficacy Endpoint(s)

The primary efficacy endpoint is radiographic progression-free survival (rPFS), which is defined as time from first dose to the radiological progression event or death.

The radiological PFS event is either radiological disease progression defined by either soft tissue tumor progression defined by RECIST 1.1, or the bone progression defined by the Prostate Cancer Clinical Trials Working Group 2 (PCWG2). The bone progression per PCWG2 is defined as a minimum of two new lesions are observed. Progression on bone scan at time points prior to or at Week 9 requires a confirmatory scan performed six or more weeks later. This confirmatory scan should demonstrate at least 2 additional new lesions (PCWG2) compared to the week 9 scan.

rPFS will be censored in the following scenarios:

- If patient has neither PD nor death, the PFS will be censored at last radiological tumor assessment date.
- If patient had PD or Death occurred more 24 weeks (168 days) after previous tumor radiological assessment. The PFS will be censored at last radiological tumor assessment date.
- If patient does not have post baseline tumor assessment, nor death within 24 weeks (168) after first dose, the PFS will be censored at Day 1.
- If patient took any new anti-cancer therapy before any PD event, the PFS will be censored at the last radiological tumor assessment date prior to the date of new anti-cancer therapy.

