6.1.4 Other Efficacy Variables

A composite endpoint of time to composite progression free survival (cPFS), defined as the earliest date of either radiologic progression, clinical progression, or death, will be analyzed. Radiologic events will be defined as described in Section 6.1.1. Date of clinical progression is the earliest onset date of any AE determined by investigator to be clinical progression.

cPFS will be censored in the following scenarios:

- If patient has no composite PD event the cPFS will be censored at last visit date.
- If patient took any new systemic anti-cancer therapy before any composite PD event, the cPFS will be censored at the last visit date prior to the date of new anti-cancer therapy.

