7.4.2 Analysis of Secondary Endpoints

Overall Survival, time to PSA progression, and time to first use of a subsequent antineoplastic therapy will be analyzed in the same manner as the primary endpoint.

PSA response rate (PSA30, PSA50, and PSA90) and objective response rate along with exact 90% confidence interval (Clopper-Pearson) will be calculated.

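### PSA30/50/90 has no cut-off at new anti-cancer therapy, unlike the SAP's progression endpoints, and its rate is planned only over patients with a post-baseline PSA

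*SAP*

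**What the plan says.** **Numerator.** SAP 6.1.2 defines the three PSA response categories by the "decline from baseline at lowest post baseline". Neither that section nor protocol 7.4.2 says when the search for the lowest value ends.

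**Other endpoints in the same SAP.** Three of them stop at new therapy:
- rPFS (SAP 6.1.1): "If patient took any new anti-cancer therapy before any PD event, the PFS will be censored at the last radiological tumor assessment date" before that therapy.
- Time to PSA progression (SAP 6.1.2): "the time to PSA progression will be censored at the PSA sample date prior to the date of new anti-cancer therapy".
- Composite PFS (SAP 6.1.4): "the cPFS will be censored at the last visit date prior to the date of new anti-cancer therapy".

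**Treatment after progression.** Protocol 2.2.1 states: "If another non-cytotoxic, non-investigational, antineoplastic agent is initiated after protocol-defined progression has been determined, enzalutamide may be continued", subject to investigator judgment and sponsor approval. Protocol 5.1.3.2 opens its prohibited list, which includes abiraterone, with: "The following medications are prohibited while patients are on enzalutamide treatment and have not had disease progression".

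**Denominator.** Protocol 7.4.2 states: "Analyses for PSA response rates will include all subjects with at least one post-baseline PSA measure". SAP 7.4.2 says only: "PSA response rate (PSA30, PSA50, and PSA90) and objective response rate along with exact 90% confidence interval (Clopper-Pearson) will be calculated". It names no denominator, but SAP 7.1 bases category percentages on subjects without missing data, which has the same effect.

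**The concern.** PSA response and time to PSA progression use the same series of PSA values. A value taken after a new drug has started is excluded from one and can count in the other, and the SAP gives no reason. If the added drug lowers PSA past a threshold for the first time, the rule as written credits that decline to enzalutamide re-treatment.

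The denominator raises a smaller question. Patients who die, withdraw consent or are lost before any post-baseline PSA leave the calculation instead of counting as non-responders.

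The trial has a single arm, so no control group is subject to the same rules. The PSA response derivation also feeds the interim report (protocol 7.8, SAP 7.10) and the PSA30 subgroup analyses (SAP 7.8).

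**Working it through.** **1. The plan's own figure.** The documents state no expected PSA response rate. The sizing figures (about 34 events, lower 90% bound about 2.5 months) concern rPFS. The event count reproduces: 40 × [1 − mean of exp(−(ln 2/4)·t) over t = 12 to 24 months] = 37.9, and 37.9 × 0.9 = 34.1. It has no bearing on PSA response.

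**2. Can a PSA be taken after new therapy and still count?**
- PSA is scheduled throughout treatment and at Safety Follow-Up (protocol Table 1 and 5.3.2).
- Enzalutamide may continue with an added agent after progression (protocol 2.2.1, 5.1.5). Footnotes b and j of protocol Table 1 foresee another antineoplastic starting before the last enzalutamide dose.
- Progression need not mean a rising PSA: starting an opioid is listed as clinical progression (protocol 2.2.1).
- Limits: for patients who stop enzalutamide, the Safety Follow-Up visit is placed before new therapy, and long-term follow-up lists no PSA (protocol 6.1).

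So the route exists, essentially only for patients who continue enzalutamide with an added agent.

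**3. Who lacks a post-baseline PSA?** Anyone who discontinues without withdrawing consent has a Safety Follow-Up visit (protocol 6.1) with PSA scheduled (Table 1, 5.3.2). That leaves mainly early deaths, consent withdrawals and losses to follow-up.

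**4. Direction.** Let n be all treated, r the patients reaching the threshold before new therapy, k those reaching it only afterwards, and m those without a post-baseline PSA. The reference is r/n, with missing PSA as non-response.
- Window: the minimum over a longer window cannot exceed that over a shorter one, so (r + k)/n ≥ r/n.
- Denominator: r/(n − m) ≥ r/n, with equality only if m = 0 or r = 0.
- Together: (r + k)/(n − m) ≥ r/n.

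**5. Size under assumed counts.** n = 40 (protocol 2.2.1); intervals are exact 90% Clopper-Pearson (SAP 7.4.2). For the range of r, protocol 1.2 cites PSA50 rates of 13% to 46% with enzalutamide after abiraterone and docetaxel, a different population: 0.13 × 40 = 5.2 and 0.46 × 40 = 18.4, rounded to 5 and 18. The values r = 8, k = 1 and m = 4 are assumptions.

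| r | Reference r/40 | One late response, (r + 1)/40 | Four without PSA, r/36 |
|---|---|---|---|
| 5 | 12.5% (5.1–24.5) | 15.0% (6.7–27.5) | 13.9% (5.6–27.0) |
| 8 | 20.0% (10.4–33.2) | 22.5% (12.3–36.0) | 22.2% (11.6–36.5) |
| 18 | 45.0% (31.5–59.1) | 47.5% (33.8–61.5) | 50.0% (35.3–64.7) |

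With r = 8 and both effects: 9/36 = 25.0% (13.7–39.6). One late response adds 1/40 = 2.5 points. Four patients without PSA add 1.4 to 5.0 points. The reference intervals are 19.4, 22.8 and 27.6 points wide.

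**6. The two rules interact.** Suppose 38 patients have a post-baseline PSA, 8 respond, and two non-responders have PSA only after new therapy. Adding the cut-off under the evaluable denominator alone moves 8/38 = 21.1% (10.9–34.8) to 8/36 = 22.2% (11.6–36.5), so the rate rises. Over all treated it stays at 8/40 = 20.0%.

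**7. Best overall response.** SAP 6.1.2 derives it across all timepoints, also with no stated cut-off. Exposure is smaller: RECIST governs the derivation, and after discontinuation imaging stops at radiographic progression or new therapy (protocol 6.1).

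**The case against.** The case against giving this much weight is strong in several respects.

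- **The denominator is prespecified.** Protocol 7.4.2 states it, and the SAP presents itself as an elaboration of the protocol. A reader might infer that the documents conflict or leave the denominator open. They do not. The full analysis set also already removes treated patients with no post-baseline evaluation, so the PSA rule removes only those with some other evaluation but no PSA. The four in the illustration do not separate these groups. This stands, and it is why the all-treated rate is proposed as an addition.
- **The direction depends on the reference.** Any subset denominator gives a rate at least as high as an all-treated rate with missing counted as failure. This stands. Under the evaluable denominator the missing cut-off can even lower the rate (step 6).
- **The route is thin.** It needs progression, sponsor approval, an eligible added agent and then a first threshold decline below the original baseline. Protocol 1.1 suggests cross-resistance between abiraterone and enzalutamide and describes a weaker PSA effect in 8 patients given abiraterone after docetaxel and enzalutamide. Protocol 5.1.3.2 (no new systemic therapy while on study) and 6.1 (removal from enzalutamide on a decision to start new therapy) read more restrictively than 2.2.1 and 5.1.5. All this limits the size, but it does not close the window in SAP 6.1.2.
- **Nothing formal depends on it.** The endpoint is secondary and descriptive, the interim is for internal review, and no threshold or stopping rule uses PSA response. This stands.

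None of this explains why new therapy ends the PSA series for one PSA endpoint and not for the other.

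**Conclusion.** The point holds as a cheap improvement. SAP 6.1.2 leaves the PSA response window open where it closes the window for rPFS, time to PSA progression and composite PFS. Followed as written, it can credit another drug's PSA decline to enzalutamide. The denominator part is real but smaller, and its direction holds only against an all-treated rate with missing PSA as non-response.

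The size rests on assumed counts: 2.5 points for one late response in 40, and 1.4 to 5.0 points for four patients without PSA. Both are small against the interval widths. The true effect is zero if every treated patient has a post-baseline PSA and no response first appears after new therapy.

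Two stronger readings go too far. A reader might infer that the PSA response rates will be inflated; the documents show only that they can be, by an unknown amount. A reader might also infer a known direction of bias in the tests of AR-V7 status against PSA response. None follows, because a late response could fall in either AR-V7 group.

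**What to change.** Adopt both changes together, because the cut-off alone can raise the evaluable-patient rate.

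(a) In SAP 6.1.2, derive PSA30/50/90 only from PSA samples taken before the first new anti-cancer therapy. Use the definition of new therapy that applies to time to PSA progression, since SAP 6.1.4 uses a narrower term (systemic therapy) for composite PFS. State the same cut-off for best overall response.

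(b) In SAP 7.4.2, also report PSA30/50/90 over all treated patients (the safety analysis set), counting those with no qualifying post-baseline PSA as non-responders. Show this beside the evaluable-patient rate of protocol 7.4.2.

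The protocol passages on starting new therapy during enzalutamide (2.2.1 and 5.1.5 against 5.1.3.2 and 6.1) should be reconciled by the sponsor; this point takes no position on which should stand.

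Cost: a few sentences in the SAP and one extra display, with no new data. Response rates may come out slightly lower.
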